## 5.5 Analysis of Efficacy Endpoints

The following efficacy related secondary endpoints will be calculated and analysed:

- Right heart catheterisation parameters
- 6-MWT, including Borg dyspnoea score
- Biomarker (NT-proBNT)
- Echocardiogram parameters
- NYHA/WHO functional class
- Quality of life (SF-36v2)

Efficacy data will be analysed exploratively. Continuous measures will be summarised using summary statistics, in addition for the changes from baseline a 95% confidence interval will be provided. Categorical variables will be summarised by using frequency counts and percentages.

### 5.5.1 Right Heart Catheterisation

Right heart catheterisation (RHC) will be performed at visit A1 and at visit MPV3 before IMP intake to determine the change of haemodynamic parameters in the patients. If available, results from a right heart catheterisation within 90 days before V1 may be used in place of the V1 measurement. The following haemodynamic parameters will be collected:

- Cardiac output (L/min) (**CO**)
- Mixed venous oxygen saturation (%) (**SvO2**)
- Pulmonary artery pressure systolic (mmHg) (**PAPs**)
- Pulmonary artery pressure diastolic (mmHg) (**PAPd**)
- Mean pulmonary artery pressure (mmHg) (**mPAP**)
- Pulmonary artery wedge pressure (mmHg) (**PAWP**)
- Right atrial pressure (mmHg) (**RAP**)
- Transpulmonary pressure gradient (mmHg) (**TPG**)
- Diastolic pressure gradient (mmHg) (**DPG**)
- Pulmonary vascular resistance (dyn\*s/cm^5) (**PVR**)
- Systemic ventricular resistance (dyn\*s/cm^5) (**SVR**)
- Cardiac index (L/min/m^2) (**CI**)
- Pulmonary arterial compliance (mL/mmHg) (**PAC, SV/PP**)
- Heart rate (bpm)
- Stroke volume (mL/beat) (**SV**)
- Stroke volume index (mL/m^2/beat) (**SVI**)

The derived parameters **mPAP**, **TPG**, **DPG**, **PVR**, **PAC**, **SV**, and **SVI** will be recalculated from other parameters using standardised formulae below.

$$mPAP = PAPd + (PAPs - PAPd)/3$$

$$TPG = mPAP - PAWP$$

$$DPG = PAPd - PAWP$$

$$PVR = (mPAP - PAWP)/CO \cdot 80$$

$$PAC = SV/(PAPs - PAPd)$$

$$SV = CO/HR \cdot 1000$$

$$SVI = CI/HR \cdot 1000$$

The recalculated parameter values will be used in summaries and listings.

The clinical significance (yes/no) of any abnormal right heart catheterisation findings will be assessed by the investigator.

**Post-DR note:** Clinical significance as assessed by the investigator will not be used for statistical analyses (see Data Review Report, Final 1.0, 10-MAR-2022). Instead, right heart catheterisation results

will be assigned a “Low”, “Normal” or “High” value according to ranges defined by Table 4. The ranges are based on the Data Validation Plan (Final 3.0, 21-JUL-2020).

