6.2 Investigational Medicinal Product

Zamicastat (also known as BIA 5-1058; 1-[(3R)-6,8-difluoro-3,4-dihydro-2H-1-benzopyran-3-yl]-1,3-dihydro-5-[2-[(phenylmethyl)amino]ethyl]-2H-Imidazole-2-thione) is currently being developed by BIAL - Portela & C^a, S.A. for the treatment of cardiovascular diseases.

Zamicastat is a reversible dopamine β -hydroxylase (DBH) inhibitor that prevents the conversion of dopamine (DA) to norepinephrine (NE) in sympathetically innervated tissues and reduces the drive of the sympathetic nervous system (SNS). Zamicastat is a peripherally-selective inhibitor as a result of its reduced ability to cross the blood-brain barrier. In contrast to what was found in peripheral tissues, zamicastat failed to affect brain levels of NE and had minimal impact on DA tissue levels in the brain, which is unique among DBH inhibitors previously tested for the treatment of cardiovascular disorders. The PD and PK profiles of zamicastat envisage a long duration of DBH inhibition, which may allow a once-daily administration. [4]

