11.4.4 Right heart catheterisation

Right heart catheterisation will be performed at visit A1, unless an RHC was performed within 90 days before visit V1 at the study site and the result of the following parameters is available: PVR, right atrial pressure (RAP), mPAP, cardiac index (CI) and mixed venous oxygen saturation (SvO₂%). Additionally, an RHC will be performed at MPV3 to determine the change of haemodynamic parameters in the patients. The RHC has to be performed before IMP intake. The following haemodynamic parameters will be determined:

- Cardiac output (CO, L/min)
- Mixed venous oxygen saturation (SvO₂%)
- Pulmonary artery pressure systolic, diastolic and mean (PAPs, PAPd and mPAP, mmHg)
- Pulmonary artery wedge pressure (PAWP, mmHg)
- Right atrial pressure (RAP, mmHg)
- Transpulmonary pressure gradient (TPG, mean PAP – mean PCWP)
- Diastolic pressure gradient (DPG, diastolic PAP – mean PCWP)
- Pulmonary vascular resistance (PVR; dyn x s x cm⁻⁵)
- Systemic vascular resistance (SVR, dyn · s/cm⁵)
- Cardiac index (CI, L/min/m²)
- Pulmonary arterial compliance (PAC; SV/PP, mL/mmHg)
- Heart rate (bpm)
- Stroke volume (mL/beat)
- Stroke volume index (mL/m²)

RHC will be performed according to the standard procedures provided in the 2015 ESC/ERS Guidelines for the diagnosis and treatment of pulmonary hypertension. [8]

If data from an RHC within 90 days before visit V1 are available, which were measured at the study site, the available data points will be transcribed to the eCRF and the procedure will not be repeated at visit A1.

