**Table 5: Right Heart Catheterisation Normal Ranges**

Parameter	Normal Range
Cardiac output (L/min) (CO)	2.5-8.0
Mixed venous oxygen saturation (%) (S v O 2 )	60-80
Pulmonary artery pressure systolic (mmHg) (PAPs)	25-80
Pulmonary artery pressure diastolic (mmHg) (PAPd)	8-16
Mean pulmonary artery pressure (mmHg) (mPAP)	≥25
Pulmonary artery wedge pressure (mmHg) (PAWP)	≤15
Right atrial pressure (mmHg) (RAP)	<14
Transpulmonary pressure gradient (mmHg) (TPG)	>12
Diastolic pressure gradient (mmHg) (DPG)	>6
Pulmonary vascular resistance (dyn*s/cm  ) (PVR)	250-1000
Systemic vascular resistance (dyn*s/cm  ) (SVR)	800-1200
Cardiac index (L/min/m  ) (CI)	>2
Pulmonary arterial compliance (mL/mmHg) (PAC; SV/PP)	0.4-3.8
Heart rate (bpm)	50-100
Stroke volume (mL/beat) (SV)	>50
Stroke volume index (mL/m  /beat) (SVI)	>30

Recalculated results will be used for applicable parameters.

The following statistical output will be provided:

Table 15.2.1.1.1 Summary of Right Heart Catheterisation Parameters by HTD – Full Analysis Set

Table 15.2.1.1.2 Summary of Right Heart Catheterization Parameters – Full Analysis Set

Table 15.2.1.1.3 Summary of Right Heart Catheterisation Parameters by HTD – Modified Full Analysis Set

Table 15.2.1.1.4 Summary of Right Heart Catheterization Parameters – Modified Full Analysis Set

The default summary statistics of RHC test results will be presented by HTD and overall at visits A1 and MPV3. The absolute change from baseline will be presented as well. For the changes from baseline a 95% confidence interval will be provided.

Table 15.2.1.1.5 Summary of Right Heart Catheterization Parameters – Modified Full Analysis Set (TAPSE Subgroups)

The default summary statistics of RHC parameters PVR, mPAP, RAP, and CI will be presented by TAPSE subgroup and overall at visits A1 and MPV3. The absolute change from baseline will be presented as well. For the changes from baseline a 95% confidence interval will be provided.

Table 15.2.1.2.1 Incidence of Right Heart Catheterisation Abnormalities – Full Analysis Set

Table 15.2.1.2.2 Incidence of Right Heart Catheterisation Abnormalities – Modified Full Analysis Set

Number and percentage of patients with abnormal values will be displayed by HTD and overall in not CS abnormal and CS abnormal categories. Percentage will be based on the number of patients at specified visit.

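### SAP 5.5.1 replaces the mPAP recorded at catheterisation with a one-third approximation, which then feeds TPG, PVR and the Table 5 classes and can leave a valid baseline non-computable

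*SAP*

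**What the plan says.** Protocol 11.4.4 lists among the parameters to be determined at catheterisation "Pulmonary artery pressure systolic, diastolic and mean (PAPs, PAPd and mPAP, mmHg"), and defines TPG from the mean PAP. SAP 5.5.1 likewise has "Mean pulmonary artery pressure (mmHg") in its list of collected parameters.

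The SAP then treats mPAP as derived. Together with TPG, DPG, PVR, PAC, SV and SVI it "will be recalculated from other parameters using standardised formulae below", the formula being "mPAP = PAPd + (PAPs - PAPd)/3". TPG is this mPAP minus PAWP, and "PVR = (mPAP - PAWP)/CO" multiplied by 80. On use, the SAP says "The recalculated parameter values will be used in summaries and listings". For the Low/Normal/High classes of Table 5, where mPAP of at least 25 mmHg counts as normal, it says "Recalculated results will be used for applicable parameters".

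The SAP gives no reason for preferring the formula and describes no output with the recorded mean. The protocol does not describe the recalculation. SAP section 8 declares no changes, and SAP 4.10 plans no imputation.

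**The concern.** Recalculating TPG, DPG, PVR, PAC, SV and SVI is sensible: each follows by definition from its components, so recalculation removes arithmetic slips and aligns sites. mPAP is different. A mean pressure is an average over the whole trace, and its highest and lowest points do not determine it. A fixed weight of one third therefore puts an approximation in place of a value already recorded, and the error passes into TPG and PVR.

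PVR and mPAP are named secondary efficacy endpoints. They are summarised with 95% confidence intervals for change and appear again in the TAPSE subgroup table. As section 5.5.1 is written, no planned summary or listing shows the recorded mean, so a reader of the report could not see what the substitution did.

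The rule also has a cost in completeness. Protocol 11.4.4 lets a catheterisation from the 90 days before V1 stand as baseline if PVR, RAP, mPAP, CI and SvO2 are available. Systolic and diastolic PAP are not on that list.

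**Working it through.** The plan states no figure to reproduce here: the sample size of 32 was not formally calculated, and no variability is given for any haemodynamic endpoint. The check carries the error through the SAP's own formulae. All values of k, pressures, PAWP, CO and SDs below are assumptions, except where a source is named.

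**Error formulae.** Let PP = PAPs - PAPd and let the true mean be PAPd + k x PP.
- Error in mPAP and in TPG = (1/3 - k) x PP.
- Error in PVR = (80/CO) x (1/3 - k) x PP.
- Over the CO range in SAP Table 5 (2.5 to 8.0 L/min), 80/CO runs from 32 to 10 dyn*s/cm5 per mmHg; at CO 4 it is 20.

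**Levels.** At 80/30 mmHg, PAWP 10, CO 4, the SAP formula gives mPAP = 30 + 50/3 = 46.7, TPG = 36.7 and PVR = 36.7/4 x 80 = 733.

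| True k | True mPAP | mPAP error | True PVR | PVR error |
|---|---|---|---|---|
| 0.28 | 44.0 | +2.7 | 680 | +53 (+7.8%) |
| 1/3 | 46.7 | 0 | 733 | 0 |
| 0.36 | 48.0 | -1.3 | 760 | -27 (-3.5%) |
| 0.40 | 50.0 | -3.3 | 800 | -67 (-8.3%) |
| 0.45 | 52.5 | -5.8 | 850 | -117 (-13.7%) |

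**Classification near 25 mmHg.** At 38/18 the formula gives 18 + 20/3 = 24.7. With k = 0.40 the true mean is 18 + 0.40 x 20 = 26.0, so a patient at or above the cut-off would be classed Low. At this pulse pressure, k from 0.28 to 0.45 gives errors of +1.1 to -2.3 mmHg, so only patients that close to 25 are affected.

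**Change, same k at both visits.** Take 80/30 going to 67/27, PAWP 10, CO 4.0 to 4.4. The formula gives changes of -6.3 mmHg and -182 dyn*s/cm5. The true changes run from -5.8 and -167 (k = 0.28) to -7.5 and -214 (k = 0.45). Most of the error in levels cancels.

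**Change, k differing between visits.** A shift of 0.05 at PP 50 and CO 4 is missed by the formula: 0.05 x 50 = 2.5 mmHg, and 2.5 x 20 = 50 dyn*s/cm5.

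**Noise in the change.** Let e be the SD of the formula error per visit, independent between visits. Then SD_total = sqrt(SD^2 + 2e^2), with half-width t(0.975, n-1) x SD_total/sqrt(n). At n = 32:

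| SD of change | e = 0 | e = 1 | e = 2 | e = 4 |
|---|---|---|---|---|
| 6 mmHg | 2.16 | 2.22 (+2.7%) | 2.39 (+10.6%) | 2.97 (+37.4%) |
| 8 mmHg | 2.88 | 2.93 (+1.6%) | 3.06 (+6.1%) | 3.53 (+22.5%) |

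At PP 50, e = 4 needs a between-visit SD of k of 4/50 = 0.08, nearly half the width of the assumed range (0.45 - 0.28 = 0.17), so the last column is an outer limit. Errors positively correlated within a patient reduce every figure.

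**Missing baseline.** With a historical catheterisation that meets Protocol 11.4.4 but has no PAPs or PAPd, the SAP formula has no inputs. Baseline mPAP is then missing, as are TPG, PVR and the changes in all three, although mPAP was recorded. How many patients this affects cannot be known from the documents.

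**The case against.** **A uniform derivation is defensible.** Baselines may be transcribed from earlier procedures at about 15 sites, and the documents do not say how sites obtained the recorded mean. A site that used the one-third rule itself would show no difference. One method at both visits also lets a stable offset cancel. This stands in part: it limits the damage to changes, but does not justify leaving the recorded mean out of the outputs. A rationale may exist in the Data Review Report or the output shells, which are not available here.

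**The size is assumed.** This stands. A reader might infer that the formula always under-reads; that follows only if every k considered lies above 1/3. Below 1/3 the sign reverses.

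**Heart rate.** A reader might infer that, because the drug "reduces the drive of the sympathetic nervous system (SNS"), heart rate will fall by MPV3 and the error will distort the treatment change. The documents do not support this. They do not link the weight to heart rate, and their heart-rate evidence is mostly negative. Protocol 6.2.2 reports no clinically relevant effect at single doses of 400 and 1200 mg. Section 6.2.1 reports none in hypertensive rats and nothing substantial after a single dose in conscious dogs. It does report lower rates in the six-month dog study, in Week 13 only, and section 6.3 cites a rat model in which a fall in pulse rate was attenuated. The point does not need this mechanism.

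**Eligibility.** A reader might infer that eligibility is compromised. It is not: Protocol 9.2 rests on the mPAP documented at catheterisation, and a summary value changes no patient's entry.

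**Falling back on the formula can be worse than the fault.** This stands for any rule that uses the formula only where the recorded mean is missing. With pressures fixed at 80/30 and k of 0.36 to 0.44, the recorded mean would be 48.0 to 52.0. Pairing it with 46.7 at the other visit creates a spurious change of 1.3 to 5.3 mmHg.

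**Conclusion.** The point holds at moderate weight. The text establishes that a recorded mPAP is replaced by an approximation, which is carried into TPG, PVR, the Table 5 classes and the outputs. It also establishes that a protocol-compliant historical baseline need not contain the formula's inputs. Neither conclusion depends on an assumed number.

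The size does. For k of 0.28 to 0.45 at 80/30 and CO 4, levels are off by +2.7 to -5.8 mmHg and +53 to -117 dyn*s/cm5, and by nothing at k = 1/3. Changes are less affected: a constant k largely cancels, and what remains is some widening of the intervals.

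Two stronger statements should be avoided. The recorded mean is not lost: it stays in the collected data and can be reanalysed. Nor do mPAP and PVR together head the endpoint list: the order is PVR, RAP, mPAP, CI, SvO2. RAP, CI and SvO2 are untouched, and TPG is not a named endpoint. All are secondary, exploratory and reported descriptively.

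**What to change.** In SAP 5.5.1:
- Take mPAP out of the recalculated list. Use the recorded catheter value at both visits, for mPAP itself and as the input to the recalculated TPG and PVR. Keep the other formulae.
- Keep the one-third value as a data check and a flagged sensitivity summary. Apply it to both visits of a patient, and never pair it with a recorded mean at the other visit.
- Show both values in the catheterisation listing, and base the Table 5 class on the recorded mean.
- State how PVR is handled when a historical catheterisation lacks PAWP or CO, since Protocol 11.4.4 does not require those either.
- Declare the derivation in section 8.

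The data are already collected. The cost is a few SAP lines, one extra listing column and one sensitivity table, plus programming changes to the derivation and the classification. The downside is that discrepant recorded means must be queried rather than overwritten. If the tables have already been produced, a sensitivity table of mPAP, TPG and PVR based on the recorded mean would be enough.

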**Table 5: Right Heart Catheterisation Normal Ranges**

Parameter	Normal Range
Cardiac output (L/min) (CO)	2.5-8.0
Mixed venous oxygen saturation (%) (S v O 2 )	60-80
Pulmonary artery pressure systolic (mmHg) (PAPs)	25-80
Pulmonary artery pressure diastolic (mmHg) (PAPd)	8-16
Mean pulmonary artery pressure (mmHg) (mPAP)	≥25
Pulmonary artery wedge pressure (mmHg) (PAWP)	≤15
Right atrial pressure (mmHg) (RAP)	<14
Transpulmonary pressure gradient (mmHg) (TPG)	>12
Diastolic pressure gradient (mmHg) (DPG)	>6
Pulmonary vascular resistance (dyn*s/cm  ) (PVR)	250-1000
Systemic vascular resistance (dyn*s/cm  ) (SVR)	800-1200
Cardiac index (L/min/m  ) (CI)	>2
Pulmonary arterial compliance (mL/mmHg) (PAC; SV/PP)	0.4-3.8
Heart rate (bpm)	50-100
Stroke volume (mL/beat) (SV)	>50
Stroke volume index (mL/m  /beat) (SVI)	>30

Recalculated results will be used for applicable parameters.

The following statistical output will be provided:

Table 15.2.1.1.1 Summary of Right Heart Catheterisation Parameters by HTD – Full Analysis Set

Table 15.2.1.1.2 Summary of Right Heart Catheterization Parameters – Full Analysis Set

Table 15.2.1.1.3 Summary of Right Heart Catheterisation Parameters by HTD – Modified Full Analysis Set

Table 15.2.1.1.4 Summary of Right Heart Catheterization Parameters – Modified Full Analysis Set

The default summary statistics of RHC test results will be presented by HTD and overall at visits A1 and MPV3. The absolute change from baseline will be presented as well. For the changes from baseline a 95% confidence interval will be provided.

Table 15.2.1.1.5 Summary of Right Heart Catheterization Parameters – Modified Full Analysis Set (TAPSE Subgroups)

The default summary statistics of RHC parameters PVR, mPAP, RAP, and CI will be presented by TAPSE subgroup and overall at visits A1 and MPV3. The absolute change from baseline will be presented as well. For the changes from baseline a 95% confidence interval will be provided.

Table 15.2.1.2.1 Incidence of Right Heart Catheterisation Abnormalities – Full Analysis Set

Table 15.2.1.2.2 Incidence of Right Heart Catheterisation Abnormalities – Modified Full Analysis Set

Number and percentage of patients with abnormal values will be displayed by HTD and overall in not CS abnormal and CS abnormal categories. Percentage will be based on the number of patients at specified visit.

Table 15.2.1.3.1 Shift Table of Right Heart Catheterisation Results – Full Analysis Set

Table 15.2.1.3.2 Shift Table of Right Heart Catheterisation Results – Modified Full Analysis Set

Shift tables showing changes in the number and frequency of patients in not CS abnormal and CS abnormal categories between baseline and MPV3 will be provided.

Listing 16.2.3.1 Right Heart Catheterisation Parameters – Enrolled Set

Values of parameters of right heart catheterisation will be listed.

### 5.5.2 6-Min Walk Test (6-MWT)

The 6-MWT is a self-paced test of walking capacity used to assess aerobic capacity and endurance. It plays a key role in evaluation functional exercise capacity, assessing prognosis and evaluating response to treatment across a wide range of respiratory diseases. The distance covered over a time of 6 minutes is used as the outcome by which to compare changes in performance capacity.

The test will be performed at visit V1 before IMP intake and at visit MPV3 before right heart catheterisation.

At screening, two attempts must be performed, separated by at least 30 minutes. The attempt in which the longer distance was covered will be considered as baseline. In case the distance covered during both attempts is equal, the first attempt will be considered as baseline.

The following parameters will be collected:

- SpO2 (%) – before and after the test
- Borg Dyspnoea score – before and after the test
- Heart rate (bpm) – before and after the test
- Lap length (m)
- Number of laps completed
- Distance covered (m)
- Time walking (min)
- Oxygen flow rate (L/min)
- Number of stops
- Time stopped (min)

The Borg Dyspnoea score is a patient-reported measure for assessing breathlessness. Symptoms of breathlessness are rated on a scale of 0-10, where 0 indicates no symptoms and 10 indicates the most severe breathlessness.

The differences in SpO2, the Borg Dyspnoea score, and heart rate between after and before the test will be calculated. These differences will be displayed as additional parameters in summaries.

The following statistical output will be provided:

Table 15.2.2.1 Summary of 6-MWT by HTD – Full Analysis Set

Table 15.2.2.2 Summary of 6-MWT – Full Analysis Set

Table 15.2.2.3 Summary of 6-MWT by HTD – Modified Full Analysis Set

Table 15.2.2.4 Summary of 6-MWT – Modified Full Analysis Set

The default summary statistics of 6-MWT test results will be presented by HTD and overall at visits V1 and MPV3. The absolute change from baseline will be presented as well. For the changes from baseline a 95% confidence interval will be provided.

Table 15.2.2.5 Summary of 6-MWT Distance – Modified Full Analysis Set (TAPSE Subgroups)

The default summary statistics of 6-MWT distance travelled will be summarised by TAPSE subgroup and overall at visits V1 and MPV3. The absolute change from baseline will be presented as well. For the changes from baseline a 95% confidence interval will be provided.

Listing 16.2.3.2-Min Walk Test – Enrolled Set

Values of parameters of 6-Min walk test will be listed.

### 5.5.3 Biomarker

Blood samples will be collected for biomarker NT-proBNP (pg/mL) evaluation at visits V1 and MPV3. NT-proBNP will be summarized in the unit ng/L for statistical output. No derivations are needed as the conversion factor between these units is 1.

The following statistical output will be provided:

Table 15.2.3.1.1 Summary of Biomarker NT-proBNP (ng/L) by HTD – Full Analysis Set

Table 15.2.3.1.2 Summary of Biomarker NT-proBNP (ng/L) – Full Analysis Set

Table 15.2.3.1.3 Summary of Biomarker NT-proBNP (ng/L) by HTD – Modified Full Analysis Set

Table 15.2.3.1.4 Summary of Biomarker NT-proBNP (ng/L) – Modified Full Analysis Set

The default summary statistics of biomarker NT-proBNP will be presented by HTD and overall at visits V1 and MPV3. The absolute change from baseline will be presented as well. For the changes from baseline a 95% confidence interval will be provided.

Table 15.2.3.2.1 Summary of Biomarker NT-proBNP (ng/L) by Pooled HTD – Full Analysis Set

Table 15.2.3.2.2 Summary of Biomarker NT-proBNP (ng/L) by Pooled HTD – Modified Full Analysis Set

Biomarker NT-proBNP will be summarised as above, with HTD pooled into “HTD < 200 mg” and “HTD 200 mg” groups.

Figure 15.2.1.1 Box-Whisker Plot of NT-proBNP by Pooled HTD – Full Analysis Set

Figure 15.2.1.2 Box-Whisker Plot of NT-proBNP by Pooled HTD – Modified Full Analysis Set

Box-whisker plots of NT-proBNP will be displayed by HTD at visits V1 and MPV3. The HTD will be pooled into “HTD < 200 mg” and “HTD 200 mg” groups. Summary statistics will be displayed below each box.

Listing 16.2.3.3 Biomarker NT-proBNP – Enrolled Set

Values of biomarker NT-proBNP will be listed.

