13.4 Statistical Methods

13.4.1 Analysis of primary pharmacokinetic endpoints

The primary analysis of this study will be the analysis of the PK parameters derived by non-compartmental analysis from the plasma drug concentration versus time using Phoenix WinNonlin v8.0 or a more recent version (Certara USA, Inc., USA). Actual sampling times will be used. The area under the plasma concentration-time curve from time zero to 24 hours post-dose will be calculated using the linear trapezoidal rule.

Summary statistics will be reported, as appropriate, using the geometric mean, arithmetic mean, standard deviation, coefficient of variation, median, minimum, and maximum.

Further details of the statistical analysis and reporting of the pharmacokinetic endpoints, such as, assessment of dose proportionality (e.g. C_{maxSS} and $AUC_{0-24hSS}$) and time to steady state using concentration trough levels, will be included in a separate SAP.

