### 4.1 General Methodology and Presentation of the Results

The default summary statistics for quantitative (continuous) variables will be

- the number of patients (n),
- mean,
- standard deviation (SD),
- coefficient of variation (%CV),
- median,
- minimum (min) and maximum (max)

for patients with data.

Mean and median will be presented to one more decimal place than the raw value. The minimum and maximum values will be presented with the same decimal precision as the raw value. SD will be reported to two decimal places greater than the original value, however no more than 3 decimal places will be presented. CV will be reported to one decimal place.

For qualitative (categorical) variables, the frequency count (n) and percentage (%) of patients with non-missing data per category will be the default frequency tabulations. Where appropriate and present, the number of missing values will be displayed as “Missing” category.

Percentage values are to be presented to one decimal place, for example, 52.3%.

The denominator used for calculation of the percentages will be specified in a footnote to the tables for clarification.

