## 4.7 Baseline Value

### Baseline value

The baseline value for a variable is defined as the last non-missing value collected before the first IMP intake, unless otherwise specified.

See section 5.4.1 Exposure to IMP for definition of first IMP intake.

**Absolute change from baseline** will be calculated as

$$\text{Absolute Change from Baseline at Visit } X = \text{Value at Visit } X - \text{Baseline Value}$$

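### NT-proBNP is summarised only as an untransformed difference; add the ratio to baseline with its interval and say what the planned interval covers

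*SAP*

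**What the plan says.** NT-proBNP is measured at V1 and MPV3 and is a listed secondary efficacy endpoint (Protocol 13.1.2.2, SAP 2.2.2.2). SAP 5.5.3 says: "The default summary statistics of biomarker NT-proBNP will be presented by HTD and overall at visits V1 and MPV3". It continues: "The absolute change from baseline will be presented as well. For the changes from baseline a 95% confidence interval will be provided". The same output is planned by HTD, by pooled HTD and overall, for the FAS and the mFAS.

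SAP 4.7 defines one change measure, the visit value minus the baseline value, so absolute change here means a signed difference in ng/L. The defaults in SAP 4.1 are n, mean, SD, %CV, median, minimum and maximum; there is no geometric mean.

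SAP 5.5 repeats the general rule that "in addition for the changes from baseline a 95% confidence interval will be provided". Neither section says whether the interval is for the mean or how it is computed.

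Other plasma measures in the study are handled proportionally. For the PK parameters, Protocol 13.4.1 says: "Summary statistics will be reported, as appropriate, using the geometric mean, arithmetic mean, standard deviation, coefficient of variation, median, minimum, and maximum". For DβH activity, Protocol 13.1.2.4 uses percent change from baseline.

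**The concern.** A positive plasma concentration that varies widely between patients often moves by a proportion of its level. If NT-proBNP behaves that way, a difference in ng/L mixes the size of the effect with the size of the baseline. A patient whose V1 value is twenty times another's contributes a change twenty times as large for the same percentage fall. The mean change and its SD are then governed by the patients with high values, and the interval widens accordingly.

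At stake is the information obtained from two samples per patient in a study planned for 32 patients, with fewer in the FAS and fewer again in the mFAS or within an HTD group. No test is planned, so the estimate and its interval are the main output for this endpoint. The interval should therefore be on a scale that suits the marker.

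**Working it through.** **No plan figure to reproduce.** The SAP states no SD, effect size or power for NT-proBNP, and the sample of 32 was not formally calculated. The values below marked as assumed are not in the documents.

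**Step 1: the two intervals.**
- Planned, read as a one-sample t-interval on the mean (assumed; the SAP does not say): d = MPV3 − V1, interval mean(d) ± t(0.975, n−1) × SD(d)/√n.
- Alternative: L = ln(MPV3/V1), interval mean(L) ± t(0.975, n−1) × SD(L)/√n, then exponentiate both limits to obtain a ratio.

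**Step 2: assumed inputs.** Lognormal V1 with log-SD 0.8-1.2; SD of the log change 0.35-0.50; n = 20-30; true geometric fall 20%, so ln(0.8) = −0.223.

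**Step 3: log-ratio interval.** This follows from the noncentral t distribution.
- Least favourable corner, n = 20, SD 0.50: standard error 0.50/√20 = 0.112; 0.223/0.112 = 2.00; t = 2.093. The interval lies wholly below no change in about 47% of trials.
- Most favourable corner, n = 30, SD 0.35: standard error 0.35/√30 = 0.064; 0.223/0.064 = 3.49; t = 2.045. The share is about 92%.

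**Step 4: absolute-scale interval, by simulation (8,000 trials per setting).** The answer depends on how the change is modelled.

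| Model for the change | Absolute scale | Log ratio |
|---|---|---|
| Log change independent of baseline | about 13-54% | about 47-92% |
| Equal log spread at V1 and MPV3 | about 20-74% | about 47-92% |

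Repeat runs move the absolute-scale limits by a point or two. The log ratio did better in every setting under both models.

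The models differ for a simple reason. Under the first, the spread grows by MPV3, and the arithmetic mean falls by less than the geometric mean: 0.8 × exp(0.35²/2) = 0.85 and 0.8 × exp(0.50²/2) = 0.91. These are falls of 15% and 9%, not 20%. Under the second, the arithmetic mean falls by the full 20%.

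**Step 5: a wider grid at n = 32.** Equal spread at both visits, log-SD of the level 0.6, 1.0 or 1.4, SD of the log change 0.3, 0.5 or 0.7, 20,000 trials per setting.

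| True fall | Absolute, range | Log ratio, range | Middle case (1.0, 0.5) |
|---|---|---|---|
| 20% | 15-94% | 41-98% | 41% against 69% |
| 30% | 33% to over 99% | 79-100% | 77% against 98% |

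The absolute scale did worse in all 18 settings. In the middle case the gap narrows from 69 − 41 = 28 points to 98 − 77 = 21 points as the fall grows from 20% to 30%. It does not narrow everywhere: at n = 16 the middle case gives 21% against 38% for a 20% fall and 46% against 76% for a 30% fall.

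**Step 6: weight of high-baseline patients.** In the same grid, the three patients with the highest V1 (3/32 = 9%) supply a median 25-27% of the summed unsigned change at log-SD 0.6, 34-36% at 1.0 and 45-47% at 1.4.

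**The case against.** The strongest reply is that the study is descriptive. SAP 5.5 says "Efficacy data will be analysed exploratively", there is no success rule, and how often an interval excludes no change measures a test that nobody plans. A fall would also stay visible: the median change is among the default statistics, levels are plotted ("Box-whisker plots of NT-proBNP will be displayed by HTD at visits V1 and MPV3") and all values are listed. In the settings of step 2 the median change was negative in at least about 95% of simulated trials, and in the wider grid in at least 92%. This stands, and it limits the severity. It does not remove the point. The SAP chose an interval as its statement of precision, and it names none for the median.

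The second reply is that skewness, variability and proportional change are all assumed. That also stands; the rates above are illustrations only.

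A reader might infer that a proportional fall would probably be missed. The documents do not support that. In the equal-spread grid the absolute-scale rate is below 50% in 5 of 9 settings for a 20% fall but in only 1 of 9 for a 30% fall. In 3 of those 6 settings the log ratio is below 50% too. The choice of scale alone turns a likely detection into a likely miss in 3 of 18 settings.

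A reader might also infer that one patient will dominate the result, or that the pooled HTD groups start from different NT-proBNP levels. The documents contain no NT-proBNP values, so neither can be asserted.

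**Conclusion.** The point holds as a cheap improvement of low to moderate severity, with moderate confidence. From the text alone, NT-proBNP change is planned only as an untransformed difference, and the parameter and method of its interval are not stated. Under the assumptions of right skew, proportional change and a t-interval on the mean, the planned interval is less precise for a proportional fall than a log-ratio interval in every setting examined. For a 20% fall with 20-30 patients, the rates are about 13-54% or 20-74%, depending on the model, against about 47-92%. The direction is consistent, but the size depends on variability that the documents do not give. The supported conclusion is that a proportional fall is less likely to be shown clearly, not that it will be missed.

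**What to change.** In SAP 5.5.3:
- Derive log(MPV3/V1). Report the geometric mean ratio to baseline with its back-transformed 95% confidence interval in Tables 15.2.3.1.1 to 15.2.3.1.4 and in Tables 15.2.3.2.1 and 15.2.3.2.2.
- Draw the box plots (Figures 15.2.1.1 and 15.2.1.2) on a log axis.
- Keep the absolute change as a descriptive row.
- State which parameter the planned 95% interval estimates and by what method.

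The cost is one derived variable, a few table rows and SAP wording; no new data are needed. If the SAP (Final 1.0, 22-MAR-2022) has already been executed, the ratio should be added and labelled as supplementary. The change does not make up for the absence of a control group: a ratio to baseline remains an uncontrolled before-after comparison.
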